9.5 Notification of deaths

Only deaths that are assessed to be caused by the IMP will be reported to the sponsor. This report will be immediate.

9.6 **Pregnancy reporting**

People who are pregnant, breastfeeding, or women planning a family will be ineligible for inclusion in the study. All pregnancies within the trial (either the trial participant or the participant's partner) will be reported to the Chief Investigator and the Sponsor using the relevant Pregnancy Reporting Form within 24 hours of notification.

Pregnancy is not considered an AE unless a negative or consequential outcome is recorded for the mother or child/foetus. Any woman who becomes pregnant during the study will be referred to the

CONFIDENTIAL

Eudra CT number 2018-000963-99

Nottingham University Hospital feto-maternal unit and study drugs will be discontinued. They will have access to the usual NHS care. If the outcome meets the serious criteria, this would be considered an SAE.

If a woman becomes pregnant during the study, then, study drugs will be discontinued and she will be referred to the feto-maternal clinic.

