9. SAFETY REPORTING

9.1 Definitions

Term	Definition							
Adverse Event (AE)	Any untoward medical occurrence in a participant to whom a							
	medicinal product has been administered, including occurrences							
	which are not necessarily caused by or related to that product.							
Adverse Reaction	An untoward and unintended response in a participant to an							
(AR)	investigational medicinal product which is related to any dose							
	administered to that participant.							

CONFIDENTIAL

IRAS: 240464

Eudra CT number 2018-000963-99

	The phrase "response to an investigational medicinal product" means						
	that a causal relationship between a trial medication and an AE is at						
	least a reasonable possibility, i.e. the relationship cannot be ruled out.						
	All cases judged by either the reporting medically qualified						
	professional or the Sponsor as having a reasonable suspected causal						
	relationship to the trial medication qualify as adverse reactions.						
Serious Adverse	A serious adverse event is any untoward medical occurrence that:						
Event (SAE)	results in death						
	is life-threatening						
	 requires inpatient hospitalisation or prolongation of existing 						
	hospitalisation						
	results in persistent or significant disability/incapacity						
	consists of a congenital anomaly or birth defect						
	Other 'important medical events' may also be considered serious if						
	they jeopardise the participant or require an intervention to prevent						
	one of the above consequences.						
	NOTE: The term "life-threatening" in the definition of "serious" refers						
	to an event in which the participant was at risk of death at the time of						
	the event; it does not refer to an event which hypothetically might						
	have caused death if it were more severe.						
Serious Adverse	An adverse event that is both serious and, in the opinion of the						
Reaction (SAR)	reporting Investigator, believed with reasonable probability to be due						
	to one of the trial treatments, based on the information provided.						
CONFIDENTIAL	Page 47 of 77						

CONFIDENTIAL

Page 47 of 77

IRAS: 240464

Eudra CT number 2018-000963-99

Suspected	A serious adverse reaction, the nature and severity of which is not							
Unexpected Serious	consistent with the information about the medicinal product in							
Adverse Reaction	question set out:							

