9.2 Operational definitions for s(AE)s or s(AR)

Known side effects of omega-3 fatty acids as listed in the section 4.8 of the Summary of Product Characteristics (https://www.medicines.org.uk/emc/product/1706) will be documented in the CRFs but will not be classed as s(AE) or s(AR) and will not be reported to the sponsor. All other side-effects will be reported.

Reference safety information: information on the safety of omega-3 fatty acids is obtained from the Summary of the Product characteristic (https://www.medicines.org.uk/emc/product/1706). All other s(AE)and s(AR) will be reported to the sponsor according to their SOPs.

Similarly, treatment which was elective or pre-planned, for a pre-existing condition not associated with any deterioration in condition, e.g. pre-planned hip replacement operation which does not lead to further complications, any admission to hospital or other institution for general care where there was no deterioration in condition, and treatment on an emergency, outpatient basis for an event **not** fulfilling any of the definitions of serious as given above and not resulting in hospital admission will not be classed as s(AE) or s(AR).

CONFIDENTIAL

Page 48 of 77

IRAS: 240464

Eudra CT number 2018-000963-99

Routinely breaking the blind in double blind trials could compromise the integrity of the trial. Breaking the blind will only take place where information about the participant's trial treatment is clearly necessary for the appropriate medical management of the participant. In all cases the Investigator would evaluate the causality and expectedness of SAEs as though the participant was receiving the active medication.

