9.3 Recording and reporting of SAEs AND SUSARs

The period of time over which AEs, ARs, SAEs, SARs and SUSARs must be recorded and reported is:

- For SAEs consent
- For ARs / SARs and SUSARs from 1st IMP dose.

As omega-3 fatty acid capsules take 28 days to have an anti-inflammatory effect, any SAEs will be monitored for 28 days after last treatment dose. If the CI becomes aware of any SARs or SUSARs after the active monitoring period end, he will still inform the sponsor.

In all cases SAEs and SARs will be reported to the Sponsor, unless they are known side effects of omega-3 fatty acids.

All **SAEs** occurring from the time of **written informed consent** until 28 days post cessation of trial treatment must be recorded on the appropriate Form and faxed to the Sponsor **within 24 hours** of the research staff becoming aware of the event. Once all resulting queries have been resolved, the Sponsor will request the original form should also be posted to the Sponsor and a copy to be retained on site.

For each **SAEs** the following information will be collected:

- full details in medical terms and case description
- event duration (start and end dates, if applicable)
- action taken

CONFIDENTIAL

Page **49** of **77**

IRAS: 240464

Eudra CT number 2018-000963-99

- outcome
- seriousness criteria
- causality (i.e. relatedness to trial drug / investigation), in the opinion of the investigator
- whether the event would be considered expected or unexpected.

Any change of condition or other follow-up information should be faxed to the Sponsor as soon as it is available or at least within 24 hours of the information becoming available. Events will be followed up until the event has resolved or a final outcome has been reached.

All SAEs assigned by the CI or delegate as both suspected to be related to IMP-treatment and unexpected will be classified as SUSARs and will be subject to expedited reporting to the Medicines and Healthcare Products Regulatory Agency (MHRA). The Sponsor will inform the MHRA, the REC and the Sponsor of SUSARs within the required expedited reporting timescales.

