9.4 Responsibilities

Principal Investigator (PI):

Checking for AEs and ARs when participants attend for treatment/follow-up.

- 1. Clinical oversight of the safety of patients participating in the trial, including an ongoing review of the risk / benefit.
- Using medical judgement in assigning seriousness, causality and expectedness [in Phase III and late Phase II CTIMPs] using the Reference Safety Information approved for the trial.
- Using medical judgement in assigning seriousness and causality and providing an opinion on expectedness [in Phase I and early Phase II CTIMPs] using the Reference Safety Information approved for the trial.

CONFIDENTIAL

Page 51 of 77

IRAS: 240464

Eudra CT number 2018-000963-99

- 4. Ensuring that all SAEs and SARs (including SUSARs) are recorded and reported to the Sponsor (with the exceptions as outlined earlier), within 24 hours of becoming aware of the event and provide further follow-up information as soon as available. Ensuring that SAEs and SARs (including SUSARs) are chased with Sponsor if a record of receipt is not received within 2 working days of initial reporting.
- 5. Ensuring that AEs and ARs are recorded and reported to the Sponsor in line with the requirements of the protocol.
- 6. Immediate review of all SUSARs.
- 7. Review of specific SAEs and SARs in accordance with the trial risk assessment and protocol as detailed in the Trial Monitoring Plan.
- Assigning Medical Dictionary for Regulatory Activities (MedDRA) or Body System coding to all SAEs and SARs.
- Preparing the clinical sections and final sign off of the Development Safety Update Report (DSUR).

Sponsor:

- Central data collection and verification of AEs, ARs, SAEs, SARs and SUSARs according to the trial protocol.
- 2. Reporting safety information to the CI, delegate or independent clinical reviewer for the ongoing assessment of the risk / benefit according to the Trial Monitoring Plan.
- Reporting safety information to the Trial Steering Committee (TSC) according to the Trial Monitoring Plan.
- Expedited reporting of SUSARs to the Competent Authority (MHRA in UK) and REC within required timelines.
- 5. Notifying Investigators of SUSARs that occur within the trial.

CONFIDENTIAL

Page 52 of 77

IRAS: 240464

Eudra CT number 2018-000963-99

Page **53** of **77**

- The unblinding of a SAE for the purpose of expedited SUSAR reporting [For double blind trials only].

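### Section 9.5 limits sponsor notification to deaths judged caused by the IMP, which contradicts the SAE definition in 9.1 and the 24-hour reporting duty in 9.3 and 9.4

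*Protocol*

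**What the plan says.** Section 9.1 lists, among the criteria that make an untoward medical occurrence a serious adverse event, that it "results in death". The criterion carries no condition on cause. In the same table, the adverse reaction entry lets either the reporting medical professional or the sponsor judge that a causal relationship is reasonably suspected.

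Section 9.2 says of the side effects listed in section 4.8 of the product characteristics that they "will be documented in the CRFs but will not be classed as s(AE) or s(AR) and will not be reported to the sponsor". It also takes out pre-planned treatment, admission for general care without deterioration, and non-serious emergency outpatient treatment.

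Section 9.3 gives the general rule: "In all cases SAEs and SARs will be reported to the Sponsor, unless they are known side effects of omega-3 fatty acids". It then fixes the window and route. The window opens when the participant signs the consent form, and SAEs after that point "until 28 days post cessation of trial treatment must be recorded on the appropriate Form and faxed to the Sponsor". The time limit is 24 hours from staff awareness.

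Section 9.4 places the duty on the principal investigator: "Ensuring that all SAEs and SARs (including SUSARs) are recorded and reported to the Sponsor (with the exceptions as outlined earlier), within 24 hours". The clock starts when the investigator learns of the event.

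Section 9.5 deals with deaths: "Only deaths that are assessed to be caused by the IMP will be reported to the sponsor". It adds: "This report will be immediate".

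**The concern.** Section 9.5 is the only section headed for deaths, so site staff looking for the rule on a death would naturally turn to it. It makes notification depend on a causality judgement already made at the site, where 9.3 and 9.4 do not.

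Three things are at stake.

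- **The sponsor's own judgement.** Section 9.1 allows the sponsor to judge relatedness independently. It cannot do so promptly for a death that is not sent to it.
- **Deaths linked to other trial-supplied medicines.** Section 7.6 supplies urate-lowering treatment and a rescue pack. Section 8.12 classes urate-lowering treatment as non-investigational, and section 7.12 acknowledges that allopurinol can rarely cause severe reactions. A death attributed to one of these products is not caused by the IMP, so 9.5 would not send it.
- **Oversight.** No DMC is convened. The section on committee roles gives the TSC the decision on stopping for safety, and 9.4 has the sponsor pass safety information to the TSC. A gap at the sponsor can carry through.

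**Working it through.** No arithmetic applies. The check is to take each kind of death and read it against both sets of rules.

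| Death | Under 9.1, 9.3 and 9.4 | Under 9.5 | Result |
|---|---|---|---|
| (a) Judged caused by the IMP, not through a listed side effect | SAE, to sponsor within 24 hours | Reported, immediately | Compatible |
| (b) Judged not caused by the IMP, first dose to 28 days after the last | SAE, to sponsor within 24 hours | Not reported | Contradiction |
| (c) After written consent, before first dose | SAE, to sponsor within 24 hours | Not reported, since it cannot be caused by the IMP | Contradiction |
| (d) Judged caused by the IMP through a listed side effect | Exempt on the wording of 9.2 and 9.3 | Reported, immediately | Contradiction in the other direction |

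**Do the exceptions in 9.4 remove the conflict?** Section 9.4 allows for exceptions outlined earlier. Section 9.5 comes after 9.4, so it is not one of them. The earlier exceptions are those in 9.2, and 9.3 repeats the one for known omega-3 side effects. None covers a death for being unrelated to the IMP or for falling before the first dose. Cases (b) and (c) therefore stand.

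**Is case (c) possible in this design?** Yes. Section 7.2 takes consent at the screening visit, before screening bloods. Section 4 randomises only after those results are reviewed, and section 7.6 dispenses the study capsules at the baseline visit. There is an interval between consent and first dose, and 9.3 includes it in the SAE window.

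**Can 9.5 be read as an addition only?** It could be meant to give IMP-caused deaths a faster route on top of the 24-hour one. Its opening restriction does not say that: it states which deaths go to the sponsor at all. Apart from case (d), the only thing 9.5 would add on that reading is the immediacy of the report, because 9.3 already sends related SAEs within 24 hours.

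**Case (d)** matters mainly for the remedy. An amendment that only pointed back to 9.3 would bring in the known-side-effect exemption and leave the status of such a death unsettled.

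**The case against.** The strongest reply is that nothing gives 9.5 precedence. The duty to report is stated several times: in 9.2 for all other serious events, in 9.3 with a form, a deadline and a window, in 9.4 with a duty to chase receipt, and in 9.9 for events up to 28 days after the last dose. Staff who follow those sections will report the death. This stands, and it limits the point to what could happen if 9.5 is followed. A reader might infer that 9.5 overrides the other sections and that unrelated deaths would go unreported. The protocol does not support that, because it contains both instructions and ranks neither.

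A second reply is that other routes exist. Section 9.10 provides annual safety update reports, 11.3 gives the sponsor direct access, and section 12 sets a monitoring plan agreed with the TSC. The sponsor is the local NHS Trust (13.9), the study has one site (section 5), and 9.4 has the TSC review safety data periodically. This also stands in part. A reader might infer that every unrelated death would be lost to the sponsor and the TSC. These routes rule out that claim, though they are slower and do not replace a 24-hour report.

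A third reply is that 9.5 governs notification and not trial data. A reader might infer that the comparison of deaths between arms would be distorted. The protocol does not support that either: data come from CRFs entered in the trial database (11.1, 11.2), 10.7 analyses all randomised participants, and 9.5 removes no death from that dataset.

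None of these replies reconciles 9.5 with 9.1, 9.3 and 9.4.

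**Conclusion.** The contradiction is real and lies in the current text. For a death judged unrelated to the IMP, and for a death between consent and first dose, the protocol gives two incompatible instructions on whether the sponsor is told. If 9.5 is followed, such a death could go without expedited reporting. The sponsor could then not exercise in time the causality judgement that 9.1 gives it, and the information it passes to the TSC could be incomplete or late.

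No figure can be put on this. The protocol states no expected death rate, and deaths may still surface in CRFs, annual reports or monitoring, so nothing is claimed about the share missed or about the between-arm comparison. The conclusion assumes only that the words of 9.5 mean what they say. If they were intended solely as an extra fast route, the text still needs correcting, because it does not express that intention. The case for changing it rests on the contradiction over the gravest safety outcome and on how little the correction costs.

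**What to change.** Delete the restriction that opens 9.5 and reconcile the section with 9.1 to 9.4. The revised 9.5 should state three things:

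1. Every death from written consent until 28 days after the last dose is an SAE and is reported to the sponsor within 24 hours of awareness, whatever the assessed cause.
2. The exemption for known side effects in 9.2 and 9.3 does not apply to deaths.
3. The immediate report for deaths assessed as caused by the IMP remains, in addition to the 24-hour report.

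A matching phrase in the exemptions of 9.2 and 9.3, excepting deaths, would keep the sections consistent.

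The cost is a short text amendment, with the sponsor deciding its category under 13.10, and probably very few extra forms in a trial of 60 participants. No treatment, endpoint, sample size or analysis changes.

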9.7 Overdose

IRAS: 240464

Information about any overdose will be placed in the deviation log, and will be reported to the study sponsor. It will be recorded in the CRFs. Overdoses can be observed from patient comment. Participants who self-report overdose with an intention to self-harm will be withdrawn from the study. Given the feasibility nature of the study, we will not exclude participants with overdose from the analysis. If an SAE is associated with the overdose, the overdose will be fully described in the SAE report form

9.8 Reporting urgent safety measures

If any urgent safety measures are taken the CI/Sponsor shall immediately and in any event no later than 3 days from the date the measures are taken, give written notice to the MHRA and the relevant REC of the measures taken and the circumstances giving rise to those measures.

9.9 The type and duration of the follow-up of subjects after adverse events.

Usual NHS care and treatment proportionate to the severity of AE and AR will be available to the study participants. The GPs of study participants will be informed of the study end. The AEs and ARs for the next 28 days after study end (last dose of IMP for that participant) will be recorded and reported. Any SUSAR related to the IMP will need to be reported to the Sponsor irrespective of how long after IMP administration the reaction has occurred.

CONFIDENTIAL

Page 54 of 77

Eudra CT number 2018-000963-99

9.10 Development safety update reports

The CI will provide (in addition to the expedited reporting above) DSURs once a year throughout the clinical trial, or on request, to the Competent Authority (MHRA in the UK), Ethics Committee, Host NHS Trust and Sponsor. The report will be submitted within 60 days of the Developmental International Birth Date (DIBD) of the trial each year until the trial is declared ended.

10 STATISTICS AND DATA ANALYSIS

10.1 Sample size calculation

The main outcome of this study is dropout rates. A sample size of 60 will be able to estimate a dropout rate of 20% or higher to within a 95% confidence interval of +/- 10%.

The other purpose of this study is to calculate the sample size of the main trial, and to get a signal of efficacy of omega-3 fatty acids. Such a study does not require a formal sample size calculation, but the sample size for a pilot trial can be justified based on published rules of thumb and expected effect size. Several rules of thumb exist and suggest that a two arm pilot trial should have between 24 and 70 participants to allow calculation of the sample size of a definitive trial (58-61). Others recommend that a pilot randomized controlled trial should have 10, 14 and 24 participants in each arm if the treatment is expected to have an effect size of 0.8, 0.5, and 0.2 respectively, using the 80% CI approach in order to accurately estimate the sample size of the main trial (61). However, the ES of omega 3 fatty acids for preventing flares of gout is not known. Thus, we propose to include 60 participants (allowing for a c. 20% drop out rate) in this study to allow us to estimate the SDp with a reasonable degree of certainty, even if the effect size is 0.2 (61).

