3.2 Outcome

Primary outcome measure: Proportion of randomized patients completing the trial

Secondary outcome measures:

 proportion of patients approached by the GP with information about the study and requested to return the reply slip to the study team, who actually

CONFIDENTIAL

Page 28 of 77

IRAS: 240464

Eudra CT number 2018-000963-99

- i. reply to Academic Rheumatology, University of Nottingham
- ii. meet the eligibility criteria
- iii. agree for screening visit
- iv. meet the eligibility criteria after checking serum uric acid and other blood tests
- v. participate in the trial
- completeness of outcome data for each flare of gout
- number of gout flares between weeks 5 and 28*
- severity of flares of gout
- duration of flares of gout
- proportion of patients who withdraw from the study due to side effects related to omega-3 fatty acids
- number of gout patients not on ULT at each GP surgery as this will allow us to decide the number of GP surgeries in the main trial
- compliance with study drugs

*Gout flares between weeks 1 and 4 will be disregarded as the anti-inflammatory effects of omega-3 fatty acids take up to 4 weeks to manifest. However, this data will be collected so that it can be analysed in the proposed study.

CONFIDENTIAL

Eudra CT number 2018-000963-99

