10.3.2 Primary outcome analysis

N (%) will be used to assess drop-out rate.

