10.7 Subject population

As this is a feasibility study, with feasibility outcomes, data for all randomised population will be analysed. When estimating a signal for efficacy of the drug, an intention to treat analysis will be performed.

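### The precision claim for dropout runs the wrong way: 60 patients give about ±10 points at a rate of 20% or lower, not 20% or higher

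*Protocol*

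**What the plan says.** Section 10.1 states that "The main outcome of this study is dropout rates" and then gives the precision: 60 patients are said to be enough to "estimate a dropout rate of 20% or higher to within a 95% confidence interval of +/- 10" per cent. It gives no formula, no interval method and no upper limit to the rate.

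Section 3.2 defines the same quantity from the other side: "Primary outcome measure: Proportion of randomized patients completing the trial". Section 10.7 sets the denominator for the feasibility outcomes: "data for all randomised population will be analysed". So the claim concerns one proportion with a denominator of 60.

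Later in section 10.1 the planning value appears: "we propose to include 60 participants (allowing for a c. 20% drop out rate"). Section 10.3.2 describes the analysis in one line: "N (%) will be used to assess drop-out rate".

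**The concern.** A proportion is least precisely estimated at 50%. Moving up from 20% towards 50% makes the interval wider, so a half-width that is only just met at 20% cannot also be met at 25%, 30% or 40%. The sentence promises that it is.

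The study is meant to supply design figures for a definitive trial, and dropout is its primary outcome. A reader who trusts section 10.1 would attach ±10 points to an observed dropout of, say, 30%, and would carry too narrow a range into the planning of the next trial.

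**Working it through.** **Inputs.** n = 60, 95% confidence, half-width 10 percentage points, dropout of 20% or higher (all section 10.1); a single proportion over all randomised patients (sections 3.2 and 10.7). Dropout and completion are complements, so they have the same half-width.

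**Formulas.** Wald half-width = 1.96 × √(p(1−p)/n). Patients needed for ±10 points = 1.96² × p(1−p) / 0.10².

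**The protocol's own figure at 20%.** 1.96 × √(0.20 × 0.80 / 60) = 1.96 × 0.0516 = 0.101, or 10.1 points. In reverse, 3.8415 × 0.16 / 0.01 = 61.5, so 62 patients. Against the stated 60 and ±10, the anchor reproduces to rounding.

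**Other rates, n = 60.** Half-widths in percentage points. For the Wilson and exact (Clopper-Pearson) methods this is half the interval length, because those intervals are not centred on the observed rate.

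| Dropout | Wald | Wilson | Exact | Patients for ±10 (Wald) |
|---|---|---|---|---|
| 10% | 7.59 | 7.74 | 8.37 | 35 |
| 15% | 9.03 | 9.01 | 9.74 | 49 |
| 20% | 10.12 | 9.98 | 10.77 | 62 |
| 25% | 10.96 | 10.73 | 11.57 | 73 |
| 30% | 11.60 | 11.31 | 12.18 | 81 |
| 40% | 12.40 | 12.03 | 12.95 | 93 |
| 50% | 12.65 | 12.26 | 13.19 | 97 |

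**Where ±10 is met.** Setting the Wald half-width to 0.10 gives p(1−p) = 0.01 × 60 / 3.8415 = 0.1562, so p = (1 ± √(1 − 4 × 0.1562)) / 2, which is 19.4% or 80.6%. The claim holds at or below 19.4% and at or above 80.6%, and fails in between. At 20% the miss is 0.1 point, which is rounding. From 25% to 50% it is 1.0 to 2.7 points.

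**Could another reading rescue the sentence?** No 95% method in the table stays within 10 points at 25% or above. A 90% Wald interval would be 9.73 points at 30% but 10.13 at 35%, and the protocol says 95%. Reading the 10% as relative to the rate does not help either: 10.1/20 is 51% of the rate at 20% dropout, and 12.7/50 is 25% at 50% dropout.

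**The case against.** The best defence is that little turns on the slip. The protocol plans for about 20% dropout, and there the claim is right to rounding. At 25% to 30% the excess is 1.0 to 1.6 points, and it is never more than 2.7. The sentence would also be true of a completion rate of 80% or higher, which may be what was meant. All of this stands as a limit on the importance of the point. It does not make the sentence true, because the sentence names the dropout rate; that completion was intended is only a guess.

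A reader might infer more than the protocol supports:

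- **That 60 is too few.** Section 10.1 has a second basis for 60. The pilot rule of thumb for an effect size of 0.2 is 24 per arm, or 48 in all, and 48 / 0.8 = 60 after 20% dropout. The sample size does not hang on the faulty sentence alone.
- **That a go/no-go decision is undermined.** The protocol sets no dropout threshold for proceeding to the definitive trial, so no such decision rule is affected.
- **That no confidence interval will be reported.** Section 10.3.2 mentions only a count and percentage, but section 10.9 refers to an agreed statistical analysis plan, which is not at hand. The interval and its method may well be specified there.
- **That precision within each arm is inadequate.** The claim and the primary outcome both concern all randomised patients. The protocol makes no claim about precision by arm.

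**Conclusion.** The precision statement in section 10.1 is wrong as written. With 60 patients, about ±10 points is delivered for dropout of roughly 20% or lower. Above that, the 95% Wald half-width rises to 11.6 points at 30% and 12.7 points at 50%. The range above 80.6%, where ±10 would hold again, is not a plausible dropout rate for planning.

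This rests on a 95% interval for a single proportion, all 60 patients in the denominator, and ±10% read as percentage points. The size of the error depends slightly on the interval method; its direction does not. It is an error in the wording of a precision guarantee, modest in effect, and it does not show that 60 is the wrong sample size.

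**What to change.** Restate the sentence in section 10.1 with one named interval method throughout, for example:

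> With 60 randomised, a dropout rate of 20% or lower is estimated to within about ±10 percentage points (95% Wald interval); at 30% and 50% the half-widths are 11.6 and 12.7 points.

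If the Wilson method is preferred, the corresponding figures are 10.0, 11.3 and 12.3 points (half the interval length). Wald half-widths should not be set beside an exact interval in the same sentence: the exact 95% interval for 12 of 60 is 10.8% to 32.3%, which reaches 12.3 points above 20% and would contradict the ±10 next to it.

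The cost is one sentence. No extra patients and no change to conduct are needed; the stated precision becomes slightly less favourable.
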